Appendix A. Protocol for stellate ganglion blockade in COVID-19 patients.

ICU/progressive care RN will follow Med-27 NM policy for peripheral nerve catheter management. APS will utilize a similarly established standard of care in managing the catheters daily, for 5 consecutive days. This includes daily rounding on the patient to assess for signs of infection, muscle weakness, voice hoarseness, hematoma, intravascular migration, local anesthetic systemic toxicity, correct medication verification, verification of pump setting, evaluation for Horner's syndrome (expected), patient education, and proper dressing coverage.

Horner's syndrome refers to a constellation of symptoms that are associated with a stellate ganglion block. These include a decreased pupil size on the affected side, delayed reaction to light on the affected side, drooping eyelid and decreased sweating on the affected side. Increased temperature and vascular dilation are also noted on the affected side with stellate ganglion block.

Schedule of events: *treatment group only

Assessment	Screening: Visit-1	Baseline, Enrollment, Randomization : (Day 0)	Treatment Day 1	Treatment Day 2	Treatment Day 3	Treatment Day 4	Treatment Day 5	EOS Discharge from hospital	Follow-up: Day 90
Inclusion/Exclusion Criteria	X								
Informed Consent Form	X								
Enrollment/Randomization	X								
Demographics	X								
Eligibility	X								
Medical History	X								
Data Collection (Vitals ect)	X	X	X	X	X	X	X	X	
Acute Pain Service		X*	X*	X*	X*	X*	X*		
Stellate Ganglion Block		X*							
CRP		X	X	X	X	X	X		
TNF-Alpha		X	X		X		X		
IL-Beta		X	X		X		X		
IL-6		X	X		X		X		
Nitric Oxide Level		X	X	X	X	X	X		
Telephone Call									X
Concomitant Medications		X	X	X	X	X	X	X	X
Adverse Events		X	X	X	X	X	X	X	X

Section 6.0 Measurement of Effect:

We will be taking *measurement of the biomarkers indicative of oxygenation, lung and proinflammatory immune response and nitric oxide* - specifically,

[figure not shown]
- a) differences in mean/median values for SGB vs SOC will be assessed at each of the study designated time points for all the continuous biomarker measures - by assessing magnitude of difference and its 95% confidence level and testing differences for statistical significance at each of the time points;
- b) Differences in mean/median values for SGB vs SOC will be assessed at treatment day 5 - adjusted for baseline levels
- c) Differences in changes from baseline levels for SGB vs SOC as measured by comparison in slope trends;
- d) Differences in frequency of adverse events for SGB vs SOC over the study period from treatment through 90 day of follow up;

Secondarily,

- e) Differences between SGB vs SOC in *frequency and time to occurrence of cardiac arrhythmias*;
- f) Differences between SGB vs SOC in frequency of *need for and duration of use mechanical ventilation and/or extracorporeal membrane oxygenation (ECMO)*;
- g) Differences between SGB vs SOC in survival experience over treatment period through 90 -day discharge follow up

Sample Size issues:

For power computations we assume that SGB will particularly have an impact in reduction of inflammatory response as measured by IL-6. Looking at a meta-analyses of IL-6 values [Ulhaq ZS, Soraya GV. Interleukin-6 as a potential biomarker of COVID-19 progression. *Med Mal Infect.* 2020;50:382–383. doi: 10.1016/j.medmal.2020.04.002. 2020/04/08] and picking the largest of studies of COVID patients [Qin C, Zhou L, Hu Z, Zhang S, Yang S, Tao Y, et al. Dysregulation of immune response in patients with COVID-19 in Wuhan, China. *Clin Infect Dis* 2020, <http://dx.doi.org/10.1093/cid/ciaa248> [pii: ciaa248].], we estimate the overall mean (SD) IL-6 for COVID-19 patients to be 21 pg/mL (30.1). Using these estimates we see that a sample of 16 patients equally randomized into SGB (n=8) and SoC (n=8) would provide sufficient power to observe magnitude of differences in mean of IL-6 from as small as about 50 pg/mL and larger with 80% power at the 5% significance level assuming 2-sided hypothesis testing. (see Power Figure). The study [Liu MH, Tian J, Su YP, Wang T, Xiang Q, Wen L. Cervical sympathetic block regulates early systemic inflammatory response in severe trauma patients. *Med Sci Monitor.* 2013;19:194–201.], indicates that SGB is capable of eliciting reductions of IL-6 between groups and from baseline of magnitudes of greater than 100 pg/mL within 72hrs of first injection.

Section 7.0 Study Parameters:

Baseline Assessments

- Current Fio₂/PaO₂ ratio
- Current type of ventilation and oxygen use
- Current production of nitric oxide via Niox
- Current blood pressure and heart rate parameters
- Labs: IL-1beta, TNF-alpha, IL-6, ABG, CRP
- Chest x-ray
- Need for mechanical ventilation or other support
- Need for pressure support

Day 1 Assessments

- Vital Signs q 6 hours (0000,0600,1200, 1800)
- FiO₂
- PaO₂ if available

- Chest x-ray – if available
- Heart rate and any arrhythmias noted via telemetry
- Evidence of successful/ongoing block
- Horner's syndrome
- Current rate of infusion
- Concomitant Medications
- Vasopressor use
- Adverse Events
- Labs: CRP, IL-1 beta, TNF-alpha, IL-6, ABG (if on vent)
- Production of nitric oxide via Niox

Day 2 Assessments

- Vital Signs q 6 hours (0000,0600,1200, 1800)
- FiO₂
- PaO₂ if available
- Chest x-ray- if available
- Heart rate and any arrhythmias noted via telemetry
- Blood gas if available
- CRP
- Evidence of successful/ongoing block
- Horner's syndrome
- Current rate of infusion
- Concomitant Medications
- Vasopressor use
- Adverse Events
- Production of nitric oxide via Niox

Day 3 Assessments

- Vital Signs q 6 hours (0000,0600,1200, 1800)
- FiO₂
- PaO₂ if available
- Chest x-ray – if available
- Heart rate and any arrhythmias noted via telemetry
- Evidence of successful/ongoing block
- Horner's syndrome
- Current rate of infusion
- Concomitant Medications
- Vasopressor use
- Adverse Events
- Labs: IL-1beta, TNF-alpha, IL-6, ABG (if on vent), CRP
- Production of nitric oxide via Niox

Day 4 Assessments

- Vital Signs q 6 hours (0000,0600,1200, 1800)
- FiO₂
- PaO₂ if available
- Chest x-ray- if available
- Heart rate and any arrhythmias noted via telemetry
- Blood gas if available
- CRP

- Evidence of successful/ongoing block
- Horner's syndrome
- Current rate of infusion
- Concomitant Medications
- Vasopressor use
- Production of nitric oxide via Niox
- Adverse Events

Day 5 Assessments

- Vital Signs q 6 hours (0000,0600,1200, 1800)
- FiO2
- PaO2 if available
- Chest x-ray-if available
- Heart rate and any arrhythmias noted via telemetry
- Evidence of successful/ongoing block
- Horner's syndrome
- Current rate of infusion
- Concomitant Medications
- Vasopressor use
- Adverse Events
- Labs: Labs: IL-1beta, TNF-alpha, IL-6, ABG (if on vent), CRP
- Production of nitric oxide via Niox

Follow-up assessment Day 90

- Survival status
- SF 36
- Adverse events
- Ongoing issues/oxygen use/rehab

Section 8.0 Drug Dosage:

There will be no dosing adjustments to the continuous perineural catheter or initial bolus injection. The dosing of the block has been reduced to the minimum effective dose.

SGB Drug doses:

Initial perineural bolus injection will include clonidine 100 mcg, decadron PF 5mg, and 0.25% bupivacaine 5 ml.

Perineural catheter:

Infusion of 0.2% bupivacaine will be initiated at 2ml/hr for 5 days.

All medications are FDA approved. Standard orders for perineural blocks will be entered into the EMR system. Pharmacy responsible for ICU/progressive care will dispense orders for the medication used in the SGB. Pharmacist in ICU/progressive care will fill Cadd pump infusion catheter once per day per standard procedure in the ICU/progressive care.

Section 9.0 Adverse Event Reporting Guidelines:

The initial procedure will be stopped and the patient will be withdrawn if any of the following occurs; vasopressor or unresponsive hypotension, intrathecal injection, pneumothorax, expanding hematoma, allergic reaction, or cardiac arrhythmias. For continuous infusions, the catheter will be removed and the patient will be withdrawn if any of the following occur: local systemic toxicity, seizure, catheter migration to intravascular or intrathecal space, expanding hematoma, vasopressor unresponsive hypotension, symptomatic bradycardia, insertion site infection. Any adverse events will be treated with Nebraska Medicine standard of care procedures. Subjects can also voluntarily withdraw at any time. The PI can also withdraw any subject that is not felt to be a suitable candidate for the study.

Serious adverse events directly related to block will result in withdrawal. Directly block related serious adverse events include: local systemic toxicity, seizure, serious allergic reaction, expanding hematoma, or catheter migration to intravascular or intrathecal space, insertion site infection. As well, patients will be withdrawn if the patient develops medication unresponsive bradycardia or hypotension. This may not be directly related to block but discontinuation of infusion may facilitate resuscitation of patient. Expected complications may include voice hoarseness, ipsilateral eyelid drooping, mild pain at site of catheter, and blurred vision. Occurrence of expected complications will not result in withdrawal from study unless demanded by the patient.

Section 10.0 Statistical Considerations:

Statistical considerations for primary objective, the analysis would include means/medians (standard errors, IQRs) at each time point - and also represented by error bars - and comparisons using t test or the Mann-Whitney U test as appropriate. Multivariate analyses using Generalized estimating equations (GEE) and to compare longitudinal changes in the two groups adjusting for confounders and as well as ANCOVA based regression to measure before and after changes. Kaplan-Meier survival methods to measure time to defined thresholds and Cox regression to assess any impact of confounders.

For safety - AE's will be assessed by providing descriptive statistics related to their frequency (summarized by occurrence, percentage of occurrence, severity, seriousness, outcome, relation to treatment, start time summary, duration of AE analysis) as well as graphically via box plots and cumulative incidence plots indicative of distributions in the two trial groups. Non-parametric methods (e.g. Fisher Exact testing) will be used to statistically compare the period frequency of events between the two groups. In general, timely analysis, by creating summaries of adverse events and other safety measurements such as relevant vital signs, ECG, Laboratory abnormal findings will be done to keep a check on the increase in intensity of observations taken at baseline and/or new findings arisen after baseline.

Secondary measures:

Occurrence of cardiac arrhythmias, need for mechanical ventilation and/or ECMO as well as overall survival will be compared using time-to-event based methods (e.g. Kaplan-meier curves). The expectation is that any non-statistically significant but implied trends will be evaluated in larger phase IIb /III trial that will follow.

Stopping Rules:

We have computed stopping rules for safety, from a statistical standpoint, standpoint based on the known background rate to help support export opinion. The stopping rules for this study are based on the prospectively accumulated safety data collected from each individual patient and utilize the hypothesis testing approach. The idea is to rule out an observed event rate that is higher than the background event rate and to stop the trial if an excessive event rate is observed. For our plan to enroll 16 subjects, we assume (based on literature) that the background rate for the known risk of our experimental intervention is 10%. Based on this we have constructed a stopping rule plan (See Table below) based on the background rate of the main Serious Adverse Drug Reaction or Event SAE/ADR of 10%.

Our DSMB is empowered to stop the trial whenever they deem fit to protect the safety of patients. However, based on our plan, the DSMB will consider adopting a stopping rule that evaluates the rate of SAE/ADR after 5 enrollments,

and thereafter with each enrollment and SAE/ADR reported will require stopping/*suspension* of trial entry if the observed rate of SAE/ADR is sufficient to reject the null hypothesis that the true SAE/ADR proportion (P) is 10% or less in favor of the (one-sided) alternative hypothesis that the true SAE/ADR proportion is more than 10%. The table below depicts the stopping guidelines. Exact binomial methods are used to compute the p values and confidence limits. One-sided lower 90% confidence limit is calculated.

Number of Subjects Enrolled in the Study	Number of SAE/ADR Needed to Reject Null Hypothesis	Observed Rate of SAE/ADR (%)	One-sided p values	Lower 90% Confidence Limit
~5	2	40%	0.0815	11.22%
6-10	3	30%	0.0702	11.58%
11-15	4	27%	0.0556	12.18%
16-20	5	25%	0.0432	12.69%

Thus, for instance, if 2+ SAE/ADR events are observed in less than and equal to 5 subjects enrolled, the lower confidence limit of 11.22% will exceed the 10% background rate. The stopping rule for safety will be triggered and the study should be suspended/stopped at the discretion of the DSMB.

Section 11.0 Records to be kept: A list of all records, including flow sheets, data collection forms/instruments, summary and evaluation forms will be locked in the study coordinator's office. The subject list will be maintained by the study coordinator. The data from the electronic medical record will be retrieved and entered into the REDCAP database by research personnel.

Section 12.0 Patient Consent: The consent form must adhere to the guidelines established by the Institutional Review Board of the University of Nebraska Medical Center. The most current version of ICF will be located in the IRB application #523-20-FB. Electronic versions of ICF will be used in the event a LAR is needed to sign consent.

Subjects and/or LAR will be approached while subject is in the ICU/progressive care. If subject is unable to participate in the consenting process, the LAR will be contact via telephone and/or video chat. Consents will be sent to LAR electronically. PI and/or Sub-I will be present for all consenting process regardless is the ICF process takes place in person or video digital presence.

The subject will be in the ICU/progressive care room. A one-on-one conversation will be had between the subject & PI/Sub-I, of approximately 30 minutes to review the ICF. Then the subject will be given time alone to read over consent and ask any additional questions. If the LAR is not present in the ICU/progressive care, the LAR will be spoken to over the telephone. An electronic ICF will be sent to the LAR prior to the phone conversation. The phone conversation will last approximately 30 minutes to review the ICF. The LAR will be instructed to hang up and read the ICF in its entirety. A return call will be placed to the LAR at a designated time. Additional questions will be answered before electronic signature is done by LAR.

Section 13.0 Study and Safety monitoring DSMB

A DSMB has been constituted that includes: [name], [name], and [name]., whose responsibility will be to review continually the safety and efficacy data, as well as the other aspects of the trials

conduct. The DSMB has been charged with making recommendations regarding early suspension or termination of age trial if there is unexpected evidence of safety concerns or dramatic intervention effect. With this particular phase, in addition to proper conduct of the trial as indicated in the protocol the DSMB will primarily be concerned with monitoring adverse effects and assessing any potential adverse events with respect to patients safety at all times and advising study continuation. The study PI will, nevertheless, still shoulder the responsibility of immediately reporting potential severe adverse effects to the DSMB and ultimately all SAEs to the IRB. Weekly or immediately - at the urgent earliest opportunity-upon each potential SAE whichever occurs first, the DSMB will review the accumulating numbers and types of severe adverse-including assessing there relatedness to study intervention and recommend any analyses by the study biostatistician-pooled , by treatment group, or disaggregated as may be requested, for review against the specified stopping rules and to advise any concerns and course of action with regard to any individual or collective patient safety. The DSMB will be supported by [name], a trained Biostatistician with long experience working with NIH study DSMBs for phase I, II and III clinical trials, and who, although a Co-I with the study, has no clinical responsibility for care with any patients at UNMC.

Section 13.0 References

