If a woman of childbearing age is enrolled as a subject and there has not been a pregnancy test during their current inpatient stay, a urine or blood pregnancy test will be performed. Pregnancy will not be allowed for this study as the drug is absorbed systemically and there are known risks to the fetus.

Section 4.0 Registration Procedure:

A prospective block randomized phase I/II two arm unblinded trial of a modified SGB protocol incorporated into Standard of Care vs UNMC standard of care Only for ARDS COVID-19 patients.

Subjects and/or Legally Authorize Representative (LAR) will be approached while subject is in the ICU/progressive care. If subject is unable to participate in the consenting process, the LAR will be contact via telephone and/or video chat. Consents will be sent to LAR electronically. PI and/or Sub-I will be present for all consenting process regardless is the ICF process takes place in person or video digital presence.

The randomization will be done by using *Stratified Permuted Block Randomization* in which sequential trial participants will be subdivided into the strata as indicated by their age-groups ie; 40-59, 60-74, 75-85 years and thereafter allocated to study group via block randomization within the strata so that the balance between age groups between the two study groups stays close to equal throughout the trial.

Section 5.0 Treatment Plan of Research Design:

A prospective block randomized phase I/II two arm unblinded trial of a modified SGB protocol incorporated into Standard of Care vs UNMC standard of care Only for ARDS COVID-19 patients.

Sixteen subjects will be enrolled. Eight in the control arm and eight in the intervention SGB arm.

Subjects will be identified on the COVID unit. The study will be explained to the subject and if the subject wishes to voluntarily participate, the ICF will be signed. If the subject is unable to sign consent, the LAR consent will be utilized. If LAR is not present, an electronic link to the consent will be sent to the LAR via email.

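### The between-arm AE comparison does not say whether expected block effects count, and only the SGB arm has a directed daily examination; if they count, the comparison tilts toward an SGB excess

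*Combined protocol and SAP*

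**What the plan says.** Section 6.0, item d, lists "Differences in frequency of adverse events for SGB vs SOC over the study period from treatment through 90 day of follow up" among the measures placed before the secondary ones. Section 10.0 gives the method: "Non-parametric methods (e.g. Fisher Exact testing) will be used to statistically compare the period frequency of events between the two groups". Neither section names an event class to be left out. Section 10.0 also plans descriptive AE summaries, including by severity, seriousness and relation to treatment.

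The trial is unblinded (Section 4.0) and controls have no sham procedure (Section 5.0). For the SGB arm, Section 5.0 describes catheter care by the Acute Pain Service: "This includes daily rounding on the patient to assess for signs of infection, muscle weakness, voice hoarseness, hematoma", continuing with systemic toxicity, Horner's syndrome and other checks. In the schedule of events the Acute Pain Service row carries the treatment-group-only asterisk on Days 0 to 5. Appendix A adds 20 minutes of bedside observation after the block and neck checks every 15 minutes for one hour.

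Section 9.0 states: "Expected complications may include voice hoarseness, ipsilateral eyelid drooping, mild pain at site of catheter, and blurred vision". The only rule attached to these is that they do not lead to withdrawal unless the patient asks for it. Section 7.0 lists Horner's syndrome on Days 1 to 5 as an item separate from adverse events.

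**The concern.** AE frequency is one of the main measures, and safety and tolerance come first in the Section 1.0 objective. Two features differ between the arms apart from any shared harm. First, the expected complications, taken as effects of the block or catheter, arise essentially only in SGB patients. Second, a specialist team looks daily for a set list of problems in that arm alone. Some of these, such as infection and weakness, can also occur in controls.

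The first feature is a real tolerability effect, and the second is detection bias. A single between-arm frequency that takes in both, together with events such as hypotension or respiratory deterioration, cannot show which of them produced a difference. The answer would also turn on an unstated recording rule: whether a drooping eyelid or a hoarse voice is entered as an AE.

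**Working it through.** The plan states no AE rate, power or sample size for this comparison, so there is no figure of its own to reproduce. The check asks how often the planned test would show a significant SGB excess when all other AEs are equally frequent in both arms.

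**Inputs from the documents.** Arm sizes (Section 5.0): "Eight in the control arm and eight in the intervention SGB arm". Test: Fisher's exact (Section 10.0). Level: "80% power at the 5% significance level assuming 2-sided hypothesis testing" is stated in Section 6.0 for IL-6 only, so 0.05 two-sided is assumed here.

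**Assumptions.** The tested quantity is the number of patients with at least one AE. The background any-AE rate b (0 to 0.9) is the same in both arms. A proportion q (0 to 1) of SGB patients has a block effect counted as an AE, independently of other events. The 10% rate in the Section 10.0 stopping rule refers to serious events or reactions and is not an all-AE rate.

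**Step 1: what is significant with 8 against 8.** For 8 against 3, the one-tail probability is C(8,3)/C(16,11) = 56/4368 = 0.0128, so two-sided p = 0.026. For 8 against 2, it is 28/8008 = 0.0035, so p = 0.007. For 8 against 4, it is 70/1820 = 0.0385, so p = 0.077. The smallest significant splits are 5 v 0 (p = 0.026), 6 v 1 (0.041), 7 v 2 (0.041) and 8 v 3 (0.026). Once four controls have an event, no SGB count is significantly higher.

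**Step 2: block effects counted.** The control rate is b and the SGB rate is 1 − (1 − b)(1 − q). Binomial probabilities are summed over all significant splits with SGB higher.

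Example with b = 0.5 and q = 0.9: the SGB rate is 1 − 0.5 × 0.1 = 0.95.
- P(8 of 8 in SGB) = 0.663 and P(at most 3 in control) = 0.363; product 0.241.
- P(7 of 8) = 0.279 and P(at most 2) = 0.145; product 0.040.
- P(6 of 8) = 0.051 and P(at most 1) = 0.035; product 0.002.
- The total is 0.283; the 5 v 0 split adds almost nothing.

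Chance of a significant SGB excess:

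| b | q = 0 | q = 0.25 | q = 0.5 | q = 0.75 | q = 0.9 | q = 1 |
|---|---|---|---|---|---|---|
| 0 | 0% | 2.7% | 36% | 89% | 99.5% | 100% |
| 0.1 | 0% | 4.1% | 30% | 75% | 94% | 99.5% |
| 0.3 | 0.6% | 4.9% | 18% | 45% | 66% | 81% |
| 0.5 | 1.1% | 3.4% | 8.7% | 19% | 28% | 36% |
| 0.7 | 0.6% | 1.1% | 2.0% | 3.5% | 4.8% | 5.8% |
| 0.9 | 0% | 0% | 0% | 0% | 0% | 0% |

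**Step 3: unequal detection alone.** True rates are equal and no block effects are counted. SGB detects every event and controls a fraction d. With d = 0.5 the chance is 0%, 2%, 9% and 18% at true rates of 0.1, 0.3, 0.5 and 0.7. With d = 0.75 it is at most 4.9%. With d = 0.25, an extreme assumption, it reaches 45% at a true rate of 0.7. The documents give no detection fraction.

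**Step 4: both sources removed.** This is the q = 0 column: at most 1.1%.

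**The case against.** The strongest reply is that the plan is under-specified rather than biased. No section says the expected complications are AEs. For Horner's syndrome the text leans the other way: Section 5.0 calls it expected, Section 7.0 keeps it apart from adverse events, and Appendix A records pupil size as part of the procedure. No pooled any-AE test is written down, and Fisher's test is only an example. That stands, and it is why the point is conditional. Even so, hoarseness, catheter-site pain and blurred vision remain unassigned. So does eyelid drooping, which is both a Horner's sign in Section 5.0 and a complication in Section 9.0. The descriptive split by relation to treatment does not alter what is tested.

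It can also be said that the asymmetry is modest. The Adverse Events row has no asterisk, so collection days match in both arms. Controls have a daily research-team contact for nitric oxide, and six-hourly vital signs and telemetry are not limited to one arm. This also stands: the difference lies in directed looking, and step 3 shows that detection alone seldom produces significance unless it is very unequal.

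A third reply is that hoarseness or site pain caused by the block is a genuine tolerability outcome. That is correct, and it argues for reporting these events visibly rather than dropping them.

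Finally, stopping rests on the SAE/ADR rule and DSMB review, not on a Fisher p-value. That limits the consequence to how the safety results are read.

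**Conclusion.** The concern holds in conditional form. The plan compares AE frequency between arms, examines one arm more closely, and does not say whether expected block effects are counted. If they are counted, the expected frequency is higher in SGB even when every other AE is equally common.

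Whether that becomes a significant result depends on two rates the documents do not give. With 90% of SGB patients affected, the chance falls from about 94% at a background rate of 0.1 to 5% at 0.7 and 0% at 0.9. These figures assume a per-patient any-AE count, independence of block effects and other events, and a two-sided 0.05 level.

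A reader might infer that an SGB excess is built in by construction. The documents do not support that: it requires a recording rule they leave open, and a high background rate leaves no room for a significant excess. A reader might also infer that neither a significant nor a null result can be interpreted. The null half does not follow, because a tilt toward an SGB excess does not explain a null result. Small arms, or a high background rate in an any-AE count, would do so, and that is a separate matter.

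**What to change.** 1. State in Sections 6.0 and 10.0 which events enter the between-arm test.
2. Name a short list of events that can arise only from the block or catheter: Horner's signs including eyelid drooping, catheter-site pain, catheter migration, procedure-site hematoma, and hoarseness and blurred vision attributed to the block. Report these as tolerability in the SGB arm only, with counts and exact 95% confidence intervals and no between-arm test.
3. Keep all SAEs in the between-arm comparison, including any listed event that is serious. Keep every event type that can occur in either arm, including infection, weakness, seizure, hypotension, bradycardia, arrhythmia and respiratory events. The list in item 2 must be explicit: a general reference to the events in Sections 5.0 and 9.0 would remove several of these from the comparison.
4. Collect the compared events in both arms from the EMR plus one identical daily AE checklist, completed at the existing daily nitric oxide contact.
5. Show the all-AE comparison descriptively alongside, so that nothing is hidden by the split.
6. Complete the unfinished Section 5.0 sentence on SGB-related adverse events at the same time.

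The cost is SAP wording and one shared form, with no added visits. The downside is slightly more data entry in both arms.

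### Section 6.0 item a tests every biomarker on every scheduled day with no primary comparison or multiplicity rule, so the chance of a false-positive biomarker result is well above 5%

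*Combined protocol and SAP*

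**What the plan says.** Section 6.0 lists the measures of effect. Item a compares SGB with standard of care for all continuous biomarkers at each designated time, "by assessing magnitude of difference and its 95% confidence level" and "testing differences for statistical significance at each of the time points". Item b compares the arms at Day 5 adjusted for baseline, and item c compares slopes. Neither b nor c is limited to one marker.

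The sample-size paragraph of the same section uses one marker only: "For power computations we assume that SGB will particularly have an impact in reduction of inflammatory response as measured by IL-6". It claims that 8 patients per arm can detect a "magnitude of differences in mean of IL-6 from as small as about 50 pg/mL", with "80% power at the 5% significance level assuming 2-sided hypothesis testing". It names no day and no baseline adjustment. Its only reference to timing is a trauma study that reported IL-6 reductions within 72 hours.

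Section 10.0 offers the t test or Mann-Whitney test at each time point, with GEE and ANCOVA in addition. It refers to a primary objective, but Section 1.0 states that objective as a list: safety, tolerance, oxygenation, lung and cardiac function, inflammatory response and nitric oxide. Neither Section 6.0 nor Section 10.0 names a primary endpoint, a testing order, a multiplicity adjustment or an exploratory status for the biomarker tests. Section 1.0 marks only the secondary objectives for confirmation in a later phase.

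**The concern.** The plan prescribes many significance tests and does not say which one answers the biomarker question. If SGB changed nothing, the report could still contain one or more nominally significant differences, and nothing in the plan would tell a reader to discount them. The trial is unblinded and the choice of marker, day and test is left open, so the result to emphasise could be chosen after the data are seen. The power claim suggests a single IL-6 comparison at a controlled 5%, but the analysis section does not hold to one.

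**Working it through.** **The plan's own figure.** Inputs from Section 6.0: SD 30.1 pg/mL, 8 per arm, two-sided 5%, difference 50 pg/mL.
- Standard error = 30.1 × √(2/8) = 15.05. Noncentrality = 50/15.05 = 3.32, with 14 degrees of freedom and critical t = 2.145.
- Power by the noncentral t distribution is 87.0%. The difference detectable with 80% power is 45.3 pg/mL.
- For a Mann-Whitney test at its worst-case efficiency of 0.864, the effective size is 8 × 0.864 = 6.9 per arm. Power is 80.8% and the detectable difference 49.5 pg/mL.

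The stated 50 pg/mL at 80% power is therefore reproduced, closely so on the Mann-Whitney basis. The plan does not say which test it used. The calculation describes a single IL-6 comparison at 5%.

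**Number of tests under item a.** From the schedule of events, leaving out baseline because a baseline difference is not an SGB effect:
- CRP, Days 1–5: 5
- Nitric oxide, Days 1–5: 5
- TNF, Days 1, 3, 5: 3
- IL-1beta, Days 1, 3, 5: 3
- IL-6, Days 1, 3, 5: 3
- Total: 19

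Oxygenation measures are not counted. Section 6.0 mentions them, but PaO2 is collected only if available.

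**Level per test.** Item a gives no significance level. Its 95% confidence level implies two-sided 5%, which is also the level in the power statement.

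**Error with no true effect.**
- Expected false positives = 19 × 0.05 = 0.95, whatever the correlation.
- Chance of at least one if independent = 1 − 0.95^19 = 62.3%.
- IL-6 alone over its three days, if independent = 1 − 0.95^3 = 14.3%.

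The tests are not independent: the same 16 patients are measured repeatedly, and the markers are related. The documents give no correlations, so these are assumed. Simulated null trials with 8 per arm, normal data, t tests and the 19-test schedule give:

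| Correlation between days, same marker | Correlation between markers | At least one p<0.05 |
|---|---|---|
| 0.3 | 0.3 | 57% |
| 0.5 | 0.3 | 54% |
| 0.7 | 0.3 | 47% |
| 0.9 | 0.3 | 36% |
| 0.9 | 0.7 | 27% |

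**Two remedies compared**, both for an unadjusted t test and a 50 pg/mL difference:
- One pre-named IL-6 test at 5%: power 87.0%, as above.
- Bonferroni over all 19 tests: level 0.05/19 = 0.0026, power 41.7%, detectable difference at 80% power 69.3 pg/mL.

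**The case against.** This is a 16-patient, unblinded phase I/II proof of concept. Its objective puts safety and tolerance first, item a puts the size of the difference and its interval before the test, and GEE models the whole course. Items a–d are also set apart from the secondary items e–g. Strict multiplicity control is partly a matter of judgement in such a trial. That stands as an argument against heavy adjustment. It does not remove the need to label the tests, since the plan orders formal testing and defers only the secondary objectives to a later phase.

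IL-6 could be read as implicitly primary because it drives the sample size. But a power assumption does not designate an endpoint, and IL-6 still has three post-baseline days as well as items b and c.

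The t test is conservative in small skewed samples. If every marker were lognormal with the mean (21) and SD (30.1) assumed for IL-6, the error per test would be about 3%. The family-wise figure would be about 25–43% for day-to-day correlation 0.5–0.9 and between-marker correlation 0–0.6. This lowers the estimate but leaves it several times the nominal 5%.

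Three stronger readings go beyond the documents:
- A reader might infer that a chance finding is more likely than not. That holds under independence or low-to-moderate correlation, but not when correlation is strong.
- A reader might add ten tests from items b and c for the five markers and treat all 29 as independent. Item b reuses the Day 5 data of item a, and item c is built from the same serial values. Only item a explicitly calls for significance testing.
- A reader might infer that a chance biomarker finding would be what launches the next trial. The sentence on later trials, "The expectation is that any non-statistically significant but implied trends will be evaluated in larger phase IIb /III trial that will follow", stands under the secondary measures in Section 10.0 (arrhythmia, ventilation, ECMO, survival). It does not concern biomarkers, and it carries forward non-significant trends.

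**Conclusion.** The concern holds in this form: the biomarker testing in Section 6.0 item a has no primary comparison, multiplicity rule or exploratory label, and its false-positive risk is well above 5%. The size is 62% as the independence figure and about 27–57% under the assumed correlations (0.3–0.9 between days, 0.3–0.7 between markers, normal data). Even the lowest of these is more than five times the nominal level. The figures rest on three assumptions: the 5% level is inferred from the 95% confidence level in item a, the correlations are not in the documents, and only the five scheduled laboratory and nitric oxide markers are counted. Patient safety and the sample size are unaffected; what suffers is the interpretation of any significant biomarker result.

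**What to change.** Before outcome data are seen, name one IL-6 comparison in Sections 6.0 and 10.0 as the sole primary biomarker test at two-sided 5%, stating the day and the analysis method. The baseline-adjusted Day 5 comparison is available within item b. The power statement specifies neither a day nor an adjustment, so the sponsor should confirm both and not treat them as already settled. Report all other markers and days, and the slope analyses, as estimates with 95% confidence intervals, labelled exploratory and without significance claims.

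This is a change of wording. N stays at 16, and the error for the primary biomarker test returns to 5%. On the plan's SD, power for 50 pg/mL is 87% by unadjusted t test, or about 81% by Mann-Whitney at worst-case efficiency. The power of a baseline-adjusted analysis depends on a correlation that the documents do not give. The cost is that the other markers lose formal significance claims. One matter remains outside this fix: the 50 pg/mL target exceeds the assumed mean of 21 pg/mL, and the sponsor should address that separately.
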